9.4.2. Secondary Analyses

Safety Analyses

The following safety evaluations will be performed:

- Monitoring for AEs
- Changes in routine clinical laboratory parameters including serum chemistry, hematology, and urinalysis
- Clinically significant changes in vital sign measurements or physical examination findings
- Changes in 12-lead ECG measurements

Safety endpoints will include AEs, clinical laboratory results (serum chemistry [including liver function parameters], hematology, and urinalysis), vital sign measurements (systolic and diastolic blood pressure and heart rate), 12-lead ECG measurements, and physical examination findings.

All safety data will be presented in the data listings. Subject demographics, medical history, and prior and concomitant medications will be summarized by group using descriptive statistics. For continuous variables, these summaries will include sample size, mean, median, SD, minimum, and maximum.

For categorical variables, the summaries will include frequencies and corresponding percentages. No inferential hypothesis testing will be performed on the safety variables.

Adverse events will be coded using the MedDRA classification system.

Treatment-emergent AEs will be defined as any AEs, regardless of relationship to investigational product, that occur after the dose of investigational product. All AEs will be summarized by group at AE onset for the overall number of AEs and the percentage of subjects who experience them. The total number of AEs will be summarized by group and overall. Listings for the subsets of SAEs and treatment-related SAEs will be provided. The number of SAEs will be summarized. The incidence of AEs will also be summarized by system organ class and preferred term.

Clinical laboratory results, vital sign measurements (systolic and diastolic blood pressure and heart rate), and 12-lead ECG results will be summarized by change from baseline. Clinical laboratory values that are outside of the reference ranges will be flagged and evaluated for clinical significance by the investigator. Any ECG abnormalities, including but not limited to a QTc >500 msec or increase in QTc from the baseline ECG of ≥ 60 msec, will be summarized by group.

Detailed descriptions of the analyses in this study will be presented in the RAP.

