On Day 1 (Period 1), subjects will receive a single 1500-mg (2×750 mg) dose of gepotidacin tablet (RC or HSWG) selected from Part 1a. On Day 1 of Period 2, subjects will receive a single 3000-mg (4×750 mg) dose of gepotidacin tablet (RC or HSWG) selected from Part 1a. There will be a washout period of at least 3 days between doses.

Subjects will remain in the clinical research unit from Day -1 until Day 3 of Period 2 after all scheduled PK and safety assessments have been completed, and will return to the clinic for a Follow-up visit approximately 5 to 7 days after the final dose of study drug. The duration of the study (from Screening to the Follow-up visit) will be approximately 41 days.

Part 3: Pharmacokinetics in Japanese Subjects - Fed State

- Treatment E: Gepotidacin 1500 mg (2 × 750 mg) RC or HSWG tablets - fed
- Treatment G: Gepotidacin 2250 mg (3 × 750 mg) RC or HSWG tablets - fed
- Treatment H: Gepotidacin 3000 mg (4 × 750 mg) RC or HSWG tablets - fed
- Treatment I: Placebo tablets - fed

On Day 1 (Period 1), subjects will be stratified by gender in a 1:1 ratio and randomly assigned (10 active: 2 placebo) to receive gepotidacin tablet (RC or HSWG) selected from Part 1a in an ascending manner (Treatments E, G, and H) on Day 1 of Periods 1, 2, and 3, respectively, or placebo. For each period, a sentinel group of up to 4 subjects will be dosed with study drug and evaluated for safety and tolerability prior to dosing the remaining subjects. There will be a washout period of at least 3 days between doses. The adverse event profiles will be reviewed before escalating to the next dose. Subjects will remain in the clinical research unit from Day -1 until Day 3 of Period 3 after all scheduled PK and safety assessments have been completed, and will return to the clinic for a Follow-up visit approximately 5 to 7 days after the final dose of study drug. The duration of the study (from Screening to the Follow-up visit) will be approximately 44 days.

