9.2. Sample Size Considerations

9.2.1. Sample Size Assumptions

Sample size is largely based on feasibility; however, some justification is provided below.

Part 1a – Relative Bioavailability:

The sample size of 24 PK parameter population subjects will be used based on feasibility to address the objectives of Part 1a of the study.

There are no estimates for the coefficient of variation (CV) of HSWG for any PK parameters. An assumed CV of 27.5% for a PK parameter implies that the sample size of 24 PK parameter evaluable subjects will provide at least 80% power to demonstrate equivalence of the PK parameter. Equivalence is demonstrated when 90% confidence interval (CI) for the ratio of Test:Reference of the PK parameter will be within 0.8 to 1.25 following log transformation.

Two different test formulations are being used in this study. No adjustment for pre-planned multiple comparisons are made.

The total sample size of 27 subjects (9 subjects in 3 sequences) will be randomized to ensure 24 PK parameter evaluable subjects with PK parameter estimates from the reference and at least one test formulation.

Part 1b – Food Effect:

A sample size of 16 subjects will be randomized (8 per sequence) based on feasibility to address the objectives of Part 1b of the study.

This sample size will ensure equivalence (as specified in sample size assumption in Part 1a) with 80% power with an assumed CV of 22%.

Part 2 – Pharmacokinetics:

A sample size of approximately 10 subjects will be used in Part 2 based on feasibility to address the objectives of Part 2 of the study.

Part 3 – Pharmacokinetics - Fed State:

A sample size of 12 subjects (ideally 6 male, 6 female) will be randomized (10 active: 2 placebo) based on feasibility to address the objectives of Part 3 of the study.

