2.3. Study Design

Overview of Study Design and Key Features							
Part 1a Relative Bioavailability							
Treatment	Cross-over						Follow-up
Capsule (reference) ^a	Period 1	Wash-out At least 3 days	Period 2	Wash-out At least 3 days	Period 3	Wash-out At least 3 days	5 to 7 days after final dose
RC and HSWG tablet ^b							
Sequence 1	A		B		C		
Sequence 2	C		A		B		
Sequence 3	B		C		A		

HSWG = high shear wet granulation, RC = related compound

a 1500 mg single dose given as 3 x 500 mg capsules (Treatment A; reference formulation) under fasted conditions

b 1500 mg single doses given as 2 x 750 mg RC (Treatment B) or HSWG (Treatment C) tablets under fasted conditions

Part 1b (Optional) Food Effect											
Treatment	Cross-over			Follow-up							
RC or HSWG tablet fasted ^a	Period 1	Wash-out At least 3 days	Period 2		5 to 7 days after final dose						
RC or HSWG tablet fed ^a											
Sequence 4	D		E								
Sequence 5	E		D								

HSWG = high shear wet granulation, RC = related compound

a 1500 mg single dose given as 2 x 750 mg tablets fasted (Treatment D) and fed (Treatment E) conditions

Overview of Study Design and Key Features

Part 2 Pharmacokinetic

Treatment	Sequence			Follow-up
RC or HSWG tablet fasted ^a	Period 1	Wash-out At least 3 days	Period 2	5 to 7 days after final dose
Sequence 6	B or C		F	

HSWG = high shear wet granulation, RC = related compound

a 1500 mg single dose given as 2 x 750-mg RC (Treatment B) or HSWG (Treatment C) tablets; 3000 mg single dose given as 4 x 750-mg RC or HSWG tablets (Treatment F), both under fasted conditions

Part 3 Pharmacokinetic – Fed State

Treatment	Sequence (EGH or III)					Follow-up
Capsule (reference) ^a	Period 1	Wash-out At least 3 days	Period 2	Wash-out At least 3 days	Period 3	5 to 7 days after final dose
RC and HSWG tablet ^b						
Sequence 7	E or I		G or I		H or I	

HSWG = high shear wet granulation, RC = related compound

a 1500 mg single dose given as 2 x 750-mg RC or HSWG (Treatment E) tablets – fed; 2250 mg single dose given as 3 x 750-mg RC or HSWG (Treatment G) tablets – fed; 3000 mg single dose given as 4 x 750-mg RC or HSWG (Treatment H) tablets – fed; or placebo (Treatment I) tablets - fed

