10.2. Appendix 2: Treatment States and Phases

10.2.1. Treatment States

Assessments and events will be classified according to time of occurrence relative to the start and/or stop date of the study treatment for the respective treatment period.

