10.2.1.2. Treatment States for AE Data

Treatment State	Definition
Pre-Treatment	AE Start Date/Time < Study Treatment Start Date/Time
On-Treatment	If AE onset date/time is on or after treatment start date/time & on or before the treatment stop date/time with 2 days lag time Study Treatment Start Date/Time ≤ AE Start Date/Time ≤ Study Treatment Stop Date/Time + 2 Days
Post-Treatment	If AE onset date/time is after the treatment stop date/time with 2 days lag time AE Start Date/Time > Study Treatment Stop Date/Time + 2 days
Onset Time	If Treatment Start Date/Time > AE Onset Date/Time = AE Onset Date - Treatment Start Date
Since First Dose (Days)	If Treatment Start Date/Time ≤ AE Onset Date/Time = AE Onset Date - Treatment Start Date +1 Missing otherwise
Duration (Days)	AE Resolution Date – AE Onset Date + 1
Drug-related	If relationship is marked 'YES' on eCRF OR value is missing

NOTES:

- If the study treatment stop date is missing then the AE will be considered to be On-Treatment.

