10.3. Appendix 3: Data Display Standards & Handling Conventions

10.3.1. Study Treatment & Sub-group Display Descriptors

Treatment Group Descriptions				
Study Part	Treatment Group		Data Displays for Reporting	
	Code	Description	Description	Order [1]
1a	A	Gepotidacin 1500 mg (3 × 500 mg) reference capsules	Reference	1
1a, 2 ^[3]	B	Gepotidacin 1500 mg (2 × 750 mg) RC tablets	RC 1500 mg	2
1a, 2 ^[3]	C	Gepotidacin 1500 mg (2 × 750 mg) HSWG tablets	HSWG 1500 mg	3
1b	D	Gepotidacin 1500 mg (2 × 750 mg) RC or HSWG tablets selected from Part 1a – fasted	RC 1500 mg Fasted or HSWG 1500 mg Fasted ^[2]	4
1b, 3	E	Gepotidacin 1500 mg (2 × 750 mg) RC or HSWG tablets selected from Part 1a – fed	RC 1500 mg Fed or HSWG 1500 mg Fed ^[2]	5
2	F	Gepotidacin 3000 mg (4 × 750 mg) RC or HSWG tablets selected from Part 1a	RC 3000 mg or HSWG 3000 mg ^[2]	6
3	G	Gepotidacin 2250 mg (3 × 750 mg) RC or HSWG tablets selected from Part 1a – fed	RC 2250 mg Fed or HSWG 2250 mg Fed ^[2]	7
3	H	Gepotidacin 3000 mg (4 × 750 mg) RC or HSWG tablets selected from Part 1a – fed	RC 3000 mg Fed or HSWG 3000 mg Fed ^[2]	8
3	I	Placebo	Placebo	9

NOTES:

1. Order represents treatments being presented in TFL, as appropriate.
2. The use of "RC" vs "HSWG" will be determined after study part 1a.
3. In part 2, one of Treatment B or Treatment C (determined after study part 1a) will be administered in period 1.

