10.11.5. Safety Tables

Safety Tables					
No.	Population	IDSL / TST ID / Example Shell	Title	Programming Notes	Deliverable [Priority]
Adverse Events					
2.1	Safety	AE1	Summary of All Adverse Events		IA [1], SAC [1]
2.2	Safety	AE1	Summary of All Drug- Related Adverse Events		IA [1], SAC [1]
2.3	Safety	AE15	Summary of Common (>=25%) Non-serious Adverse Events by System Organ Class and Preferred Term (Number of Subjects and Occurrences)		IA [1], SAC [1]
2.4	Safety	AE16	Summary of Serious Adverse Events by System Organ Class and Preferred Term (Number of Subjects and Occurrences)		IA [1], SAC [1]
Laboratory Measurements					
2.5	Safety	LB1	Summary of Clinical Chemistry Change from Baseline		SAC [1]
2.6	Safety	LB1	Summary of Haematology Change from Baseline		SAC [1]
2.7	Safety	UR3b	Summary of Urinalysis Dipstick Results		SAC [1]
Electrocardiograms					
2.8	Safety	EG1	Summary of ECG Findings		SAC [1]
2.9	Safety	SAFE_T1	Summary of Frequency of Maximum Post-Dose ECG Parameter Corrected QTc Interval		SAC [1]
2.10	Safety	SAFE_T2	Summary of Frequency of Maximum Change from Baseline for ECG Parameter Corrected QTc Interval		SAC [1]
2.11	Safety	EG2	Summary of Change from Baseline in ECG Values		SAC [1]
Vital Signs					
2.12	Safety	VS1	Summary of Change from Baseline in Vital Signs		SAC [1]

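### As specified, the Part 3 adverse event summaries would set placebo incidence over three dosing periods beside one-period incidence for each fed dose

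*Protocol*

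**What the plan says.** The general rule for AE summaries is in Protocol 9.4.2: "All AEs will be summarized by group at AE onset for the overall number of AEs and the percentage of subjects who experience them". That section does not define group and leaves the detail to the reporting plan. It also rules out inferential testing of safety variables.

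The Part 3 design is fixed-sequence. The SAP 2.3 schematic heads the treatment columns "Sequence (EGH or III", so a placebo subject has three placebo periods. Protocol 4.2 has gepotidacin given "in an ascending manner (Treatments E, G, and H) on Day 1 of Periods 1, 2, and 3, respectively, or placebo", so each active dose occupies exactly one period. On numbers, Protocol 9.2.1 says: "A sample size of 12 subjects (ideally 6 male, 6 female) will be randomized (10 active: 2 placebo) based on feasibility".

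SAP 10.3.1 supplies the reporting labels. Treatments E, G and H (1500, 2250 and 3000 mg fed) each have their own descriptor; treatment I has the single descriptor Placebo. The note under that table reads: "Order represents treatments being presented in TFL, as appropriate".

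SAP 10.2.1 places events in time "relative to the start and/or stop date of the study treatment for the respective treatment period", and SAP 10.2.1.2 defines on-treatment as "Study Treatment Start Date/Time ≤ AE Start Date/Time ≤ Study Treatment Stop Date/Time + 2 Days". The AE tables in SAP 10.11.5 (2.1 to 2.4) carry no programming note on splitting placebo, on the denominator or on unequal exposure.

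**The concern.** A percentage of subjects with at least one event rises with the number of occasions on which an event can occur. If placebo subjects contribute three dosing periods to one column and active subjects one period to each of three columns, the columns measure different things under the same title.

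The direction is unhelpful for a safety display. A placebo figure inflated in expectation makes each dose look closer to placebo, or better than it. The event count does not correct this by itself, because it too accumulates over three dosings per placebo subject. A descriptive table is read by eye, so it depends on its columns being comparable, and Part 3 is the only part of the study with a placebo group.

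**Working it through.** The plan states no AE rate and no calculation on this point, so there is no figure to reproduce. The check is of the mechanism and its possible size.

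**Inputs from the documents**
- Placebo periods per subject: 3 (SAP 2.3).
- Periods per active dose per subject: 1 (Protocol 4.2).
- Part 3 subjects: 10 active, 2 placebo (Protocol 9.2.1).
- Display labels: three for fed doses, one for placebo (SAP 10.3.1).
- On-treatment window: dose to dose plus 2 days (SAP 10.2.1.2), so three windows feed the placebo label and one feeds each dose label.

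**Assumptions**
- p, the probability that a subject has at least one AE in a dosing period, is not in the documents. Values of 0.10, 0.20 and 0.30 are used.
- p is the same in every period and the same on drug and placebo (no drug effect).
- Within-subject correlation ρ between periods lies between 0 and 1.

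**Expected percentage of subjects with an AE**
- Active column, one period: p.
- Placebo column, independent periods: 1 − (1 − p)³. For p = 0.20 this is 1 − 0.8³ = 1 − 0.512 = 0.488.
- Placebo column, correlated periods (beta-binomial): with s = 1/ρ − 1, a = ps and b = (1 − p)s, it is 1 − [b/(a+b)] × [(b+1)/(a+b+1)] × [(b+2)/(a+b+2)]. For p = 0.20 and ρ = 0.5, s = 1, a = 0.2 and b = 0.8, giving 1 − 0.8 × 0.9 × 0.933 = 0.328.
- Placebo column, perfect correlation: p.

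| p | Active column | Placebo, ρ = 0 | ρ = 0.2 | ρ = 0.5 | ρ = 1 |
|---|---|---|---|---|---|
| 0.10 | 10% | 27.1% | 22.7% | 17.3% | 10% |
| 0.20 | 20% | 48.8% | 41.8% | 32.8% | 20% |
| 0.30 | 30% | 65.7% | 57.4% | 46.5% | 30% |

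Under independence the ratio of placebo to active is 2.71, 2.44 and 2.19 for p = 0.10, 0.20 and 0.30. It stays below 3 and falls to 1 at ρ = 1.

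**What the table could actually show**
- With 2 placebo subjects the column takes only the values 0, 50 and 100%.
- At p = 0.20 with independent periods, the chance that at least one of the 2 is counted is 1 − 0.8² = 36% over one period and 1 − 0.512² = 73.8% over three.
- The chance that neither is counted over three periods is 0.8⁶ = 26% at p = 0.20 and 0.9⁶ = 53% at p = 0.10. At p = 0.10, 0% is therefore the likeliest placebo result even in the pooled column.

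**With placebo shown by period**, each placebo column covers one dosing per subject, and its expected percentage returns to p whatever the correlation.

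**The case against.** The strongest reply is that the layout is inferred. Protocol 9.4.2 speaks only of groups, SAP 10.3.1 is a list of labels to be used as appropriate, and the table shells are not in the text available for review. Events are placed by treatment period, so a programmer could split placebo without departing from the plan. This stands: the plan does not forbid a split. But it does not ask for one either, and the labels as written lead to a single column.

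The second reply is that the size depends on independence between periods. That also stands, which is why the result is given as a range ending at no inflation.

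The third is that little hangs on it. There is no inferential testing. Dose escalation rests on review of AE profiles as the study proceeds, in blinded aggregate unless a signal is suspected (Protocol 6.4), not on the final percentages. The AE and exposure listings (SAP 10.11.8, Listings 14 and 11) allow per-period results to be rebuilt for two people. All of this limits the weight of the point; none of it makes the columns comparable.

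Two stronger readings are tempting and are not supported:
- A reader might infer that this undermines the stated reason for Part 3. Protocol 4.4 and the Amendment 2 rationale in Appendix 11 frame that reason as whether a meal makes the larger doses better tolerated than when fasted. That compares treatment F in Part 2 with treatment H in Part 3, and each covers one dosing period per subject, so it is untouched.
- A reader might infer that placebo by period would reveal a time trend behind any rise across the ascending doses. Dose is tied to period by design, and 2 placebo subjects per period could not establish a trend.

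**Conclusion.** The point holds as a minor flaw in the specified display. A cumulative three-period placebo incidence would sit beside one-period incidences for the three fed doses. With no drug effect and an assumed per-period AE probability of 0.20, the placebo column expects 20% to 48.8% against 20% per dose, depending on how strongly a subject's periods are correlated. At 0.10 and 0.30 the upper ends are 27.1% and 65.7%.

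This rests on the single placebo label in SAP 10.3.1 being carried into Tables 2.1 to 2.4, which the documents suggest but do not show in a shell. The effect is a tendency to mask a drug effect, not a prediction for this trial: two subjects give a coarse percentage that may well be 0%. No decision rule or test is affected.

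**What to change.** In the Part 3 AE tables, show placebo by period (P1, P2, P3) beside 1500, 2250 and 3000 mg fed respectively. Keep the pooled placebo column as an addition, with a footnote that it covers three dosing periods per subject. A line in SAP 10.3.1 and a programming note on Tables 2.1 to 2.4 would suffice.

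A denominator of subject-periods (2 × 3 = 6 for placebo, 10 for each dose) would also equalise exposure, but it counts repeats from two people as separate units, so the by-period columns are preferable.

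The cost is three sparse columns with n = 2 each, still reading only 0, 50 or 100%. No new data and no design change are needed. The split does not cure the small numbers. In the table titled "Summary of Common (>=25%) Non-serious Adverse Events by System Organ Class and Preferred Term (Number of Subjects and Occurrences", for example, one placebo subject with a given term reads 50% in a pooled or a by-period column, so the cut-off is passed either way if it is applied column by column, which the plan does not specify.

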5.4.3. Gastrointestinal Stopping Criteria

Subjects experiencing Grade 3 or Grade 4 AEs (confluent pseudomembranes or ulcerations OR mucosal bleeding with minor trauma; tissue necrosis OR diffuse spontaneous mucosal bleeding OR life-threatening consequences, e.g., aspiration, choking) will be followed as appropriate until resolution of the AE(s).

Furthermore, subjects who experience diarrhea or enteritis should be evaluated with additional fecal occult blood tests and stool cultures as deemed appropriate by the investigator as outlined in [Appendix 8](#) and [Appendix 9](#).

For Part 3, subjects who experience diarrhea should also be evaluated using the guidelines detailed in [Table 8](#)

Table 8 Part 3 Management of Gastrointestinal Symptoms - Diarrhea

Diarrhea	Treatment Strategy
Grade 1	Initiate supportive care including loperamide.
Grade 2	Initiate supportive care including loperamide. Consider discontinuation of subject from the study upon discussion with medical monitor.
Grades 3 or 4	Above plus consider IV hydration, hospital admission and prophylactic antibiotics as appropriate. Withhold study drug(s) until diarrhea has resolved to ≤Grade 1, continue diarrheal prophylaxis. Discontinue subject from the study upon discussion with medical monitor.

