- If a subject dies during participation in the study or during a recognized follow-up period, the investigator will provide GSK with a copy of any postmortem findings, including histopathology.
- New or updated information will be recorded in the originally completed eCRF.
- The investigator will submit any updated SAE data to GSK within the designated reporting time frames.

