Constipation	Requiring stool softener or dietary modification	Requiring laxatives	Obstipation requiring manual evacuation or enema	Obstruction or toxic megacolon
Diarrhea	Mild or transient; 3 to 4 loose stools/day or mild diarrhea lasting <1 week	Moderate or persistent; 5 to 7 loose stools/day or diarrhea lasting >1 week	>7 loose stools/day or bloody diarrhea; or orthostatic hypotension or electrolyte imbalance or >2L IV fluids required	Hypotensive shock or physiologic consequences requiring hospitalization
Oral discomfort/Dysphagia	Mild discomfort; no difficulty swallowing	Some limits on eating/drinking	Eating/talking very limited; unable to swallow solid foods	Unable to drink fluids; requires IV fluids

IV = intravenous.

NEUROLOGICAL				
	Grade 1	Grade 2	Grade 3	Grade 4
Neuro-cerebellar	Slight incoordination dysdiadochokinesis	Intention tremor, dysmetria, slurred speech; nystagmus	Locomotor ataxia	Incapacitated
Psychiatric	Mild anxiety or depression	Moderate anxiety or depression; therapy required; change in normal routine	Severe mood changes requiring therapy; or suicidal ideation; or aggressive ideation	Acute psychosis requiring hospitalization; or suicidal gesture/attempt or hallucinations
Muscle strength	Subjective weakness; no objective symptoms/signs	Mild objective signs/symptoms; no decrease in function	Objective weakness; function limited	Paralysis
Paresthesia (burning, tingling, etc)	Mild discomfort; no treatment required	Moderate discomfort; non- narcotic analgesia required	Severe discomfort; or narcotic analgesia required with symptomatic improvement	Incapacitating; or not responsive to narcotic analgesia
Neurosensory	Mild impairment in sensation (decreased sensation, e.g., vibratory, pinprick, hot/cold in great toes) in focal area or symmetrical distribution; or change in taste, smell, vision, and/or hearing	Moderate impairment (moderately decreased sensation, e.g., vibratory, pinprick, hot/cold to ankles) and/or joint position or mild impairment that is not symmetrical	Severe impairment (decreased or loss of sensation to knees or wrists) or loss of sensation of at least moderate degree in multiple different body areas (i.e., upper and lower extremities)	Sensory loss involves limbs and trunk; paralysis; or seizures

MUSCULOSKELETAL				
	Grade 1	Grade 2	Grade 3	Grade 4

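### AEs are assigned to a dose by onset alone, so in Parts 2 and 3 an AE that persists into the next, higher dose and worsens there can be missing from the higher-dose column

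*Protocol*

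**What the plan says.** **Attribution.** Protocol 9.4.2: "All AEs will be summarized by group at AE onset for the overall number of AEs", together with the percentage of subjects affected. The same section defines a treatment-emergent AE by its occurrence after the dose, with nothing about worsening. SAP 10.2.1 classifies events "relative to the start and/or stop date of the study treatment for the respective treatment period", so the unit is the period and hence the dose. SAP 10.2.1.2 defines on-treatment as "If AE onset date/time is on or after treatment start date/time & on or before the treatment stop date/time with 2 days lag time". An AE that starts before the period's dose is pre-treatment. Each AE has one onset date and one resolution date.

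**Recording.** Protocol 12.5.4 says of follow-up: "New or updated information will be recorded in the originally completed eCRF". It asks for an intensity assessment for each AE but does not say whether this is at onset, the maximum, or by period. Protocol 12.5.1 includes among AEs a rise in frequency or intensity of a chronic or intermittent condition that existed beforehand.

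**Tables.** SAP 10.11.5 plans four AE tables: all (2.1), drug-related (2.2), common non-serious at 25% or more (2.3) and serious (2.4). None is by severity.

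**Design.** Part 2 gives 1500 mg then 3000 mg to about 10 subjects. Part 3 gives 1500, 2250 and 3000 mg in ascending order to 10 active subjects, with 2 on placebo. Doses are at least 3 days apart (protocol 4.1, 4.2, 4.3, 9.2.1).

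**The concern.** Safety and tolerability by dose is a stated secondary objective of Parts 2 and 3 (protocol section 3). Section 4.4 adds that Part 3 will look at whether food improves tolerability at higher doses. The AE counts by dose are the main summary that answers this.

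When the dose order is fixed and ascending, an onset-only rule errs in one direction. An AE can begin under a lower dose and worsen under a higher one, but the reverse order never occurs. If the worsening is entered as an update to the first record, the higher-dose column has no trace of it. The lower-dose count is not wrong, since the event did begin there; the omission is at the higher dose. No planned table shows grade by dose, so the worsening would surface only in the listings, and only if its date was recorded.

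**Working it through.** The plan gives no figure on this point, so there is nothing to reproduce. The check is to trace one hypothetical subject through the rules and then size the effect.

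**1. Tracing the rules.** A Part 3 subject has Grade 1 loose stools after 1500 mg. They are still present at the 2250-mg dose and become Grade 3 after it.

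| Site action | Onset date | State in the 2250-mg period (SAP 10.2.1.2) | Counted under 1500 mg | Counted under 2250 mg |
|---|---|---|---|---|
| Updates the original record | before 2250 mg | pre-treatment | yes | no |
| Opens a new record at worsening | after 2250 mg | on-treatment, if within the 2-day lag | yes | yes |

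The same clinical course gives different counts, and neither document says which action applies. Protocol 12.5.4 can be read as requiring the first and 12.5.1 as requiring the second.

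**2. Do the safeguards close the path?** Protocol 4.6.1 has permanent discontinuation for Grade 3 or 4 events (GI row), which concerns events already at that grade. The path here starts at Grade 1 or 2. For those grades, Table 8 in protocol 5.4.3 gives supportive care, and at Grade 2 consideration of discontinuation. Neither entry makes resolution a condition of the next dose. The AE review before each Part 3 escalation states no such condition either. The path is narrowed but open.

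**3. Size per subject.** With n = 10 active subjects, one omitted subject changes the incidence by 1/10 = 10 percentage points, provided that subject has no other AE counted in the same row for that period.

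- 1/10 (10%) becomes 0/10 (0%).
- 3/10 (30%) becomes 2/10 (20%), which falls below the 25% cut of Table 2.3 if the cut is applied by dose column. The SAP title does not say how it is applied.

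**4. Chance of at least one such subject.** Let p be the probability, per subject and per escalation, that an AE persists to the next dose, the subject is dosed, and the AE then increases in grade. The documents give no value for p, so these are assumptions. With m subject-escalations treated as independent, the chance is 1 − (1 − p)^m. Here m = 10 × 1 = 10 in Part 2 and 10 × 2 = 20 in Part 3.

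| Assumed p | Part 2: 1 − (1 − p)^10 | Part 3: 1 − (1 − p)^20 |
|---|---|---|
| 0% | 0% | 0% |
| 1% | 9.6% | 18.2% |
| 5% | 40.1% | 64.2% |
| 10% | 65.1% | 87.8% |

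These are chances that the situation arises at all. A miscount also requires that the site updates the old record.

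**The case against.** The case against has four parts.

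- **The recording rule is inferred.** A reader might take the protocol to direct that a grade rise is written into the original record. It does not. The sentence in 12.5.4 is general, does not mention grade, and stands beside text on postmortem findings and SAE updates. The clause in 12.5.1 could lead a site to open a new AE. The counter-argument, that an AE which began after an earlier study dose is not naturally a pre-existing condition, is reasonable but not decisive. This objection stands: the defect is an unspecified rule, not a stated rule that forces the miscount.
- **Persistence is not shown.** A reader might infer that dosing over an ongoing AE is to be expected, because Appendix 6 grades as mild "3 to 4 loose stools/day or mild diarrhea lasting <1 week". That is a grading definition, not evidence of duration. Section 4.6.1 links the cholinergic effects, diarrhea among them, to Cmax. With the half-life of 12.0 h in protocol Table 5, 72 h is 72/12 = 6 half-lives, leaving 0.5^6 = 1.6% of the drug. Nor may Table 8 be read only as "Withhold study drug(s) until diarrhea has resolved to" Grade 1 or less, because the same cell goes on to discontinuation from the study after discussion with the medical monitor. This stands too: how often the path occurs is unknown.
- **Individual data remain.** Safety is descriptive, and all AEs, AEs leading to withdrawal, and exposure are listed (Listings 14, 17, 11). With 10 active subjects the listings can be read one by one. This reduces the harm but does not make the tables right, and it helps only if the change in grade is dated.
- **Onset counting is a clear convention**, and counting a continuing event under two doses has its own attribution problem. True, but a footnote deals with that, whereas an omitted worsening cannot be recovered from the tables.

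A reader might also extend the point to Part 1a, where B always follows A, C follows B and A follows C. The documents do not support a systematic shift there. Each formulation appears once in each period, each follows another in two of the three sequences, and every dose is 1500 mg. Any omission affects all three alike unless persistence or worsening differs by formulation.

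**Conclusion.** The point holds in a conditional form. Attribution is by onset only, no clause covers worsening, and no rule tells the site how to record a grade rise after a later dose. In Parts 2 and 3 any resulting miscount understates the higher dose. One subject is worth up to 10 percentage points.

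It rests on four conditions: an AE lasts to the next dose, the subject is dosed, the AE then increases in grade, and the site updates the old record. If no AE persists and worsens there is no bias.

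A reader might want a modelled figure for how far the dose-tolerability relation is flattened. The documents give no rates, and any model result turns on assumptions they do not settle, such as whether a subject with an ongoing AE can also have a new one. The size should therefore be left at the per-subject figure. The primary PK results are not affected. The change is worth making because it is cheap, serves a stated objective, and depends on dates that may not be recoverable afterwards.

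**What to change.** 1. In protocol 9.4.2 and SAP 10.2.1.2, define an AE as treatment-emergent for a dose if it starts, or increases in DMID grade, after that dose and before the next dose (or Follow-up). This window is longer than the SAP's 2-day lag, so the SAP should state that it governs the AE tables.
2. Use this definition for SAP Tables 2.1 to 2.4 in Parts 2 and 3, counting the subject under every dose for which it holds. Add a footnote separating subject counts from event counts.
3. Instruct sites to record the date of any grade increase after a later dose, or to enter a linked new AE record, and say that this takes precedence over the general instruction in protocol 12.5.4. Apply it prospectively in Part 3. In Part 2, whose tolerability results were already known at Amendment 2, apply it where the record dates the change.

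The cost is one definition in each document and one eCRF completion instruction. The downside is that a continuing event can appear under two doses, which the footnote must explain. No dosing or clinical management rule changes.
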